2.2. Rationale

Although secondary AP is utilized in dental offices for multiple clinical scenarios, the nature of patient populations, the number of patients involved, and the frequency of use are unclear. In addition, it is not clear what guidelines dental practitioners use when making decisions about the use of AP for these varied patient populations, or the factors that influence their opinions and clinical practice. Consequently, the overall purpose of this study is to gain a better understanding of the opinions, knowledge base and clinical practice related to the use of AP for specific patient populations undergoing dental procedures.

2.3. Potential Risks and Benefits

This study consists of a cross-sectional, single time point self-report assessment of dental providers. The study (survey) will involve National Network dentists only and will not include patient recruitment. National Network member general dentists and specialists who are eligible to participate in Network surveys will be invited to participate without exclusion based on race, ethnicity, gender, or age.

2.3.1 Potential Risks

This study poses minimal risk to subjects. Study participation is completely voluntary and participants may discontinue participation at any time without prejudice. As with any study, there is the potential for loss of confidentiality. Appropriate precautions will be taken to mitigate this risk. These include the use of unique study codes for participants and password-protected computers and secure networks for data storage. Compliance with all Institutional Review Board (IRB) regulations concerning data collection, data storage, and data destruction will be strictly observed. Data will only be accessible to research personnel and will be stored and coded according to guidelines set forth by the overseeing IRB.

2.3.2 Potential Benefits

There is no direct benefit to participating dentists but they have the potential to benefit from their reflection on their own knowledge of risk mitigation strategies in AP prescribing as they respond to items on the survey. As an indirect benefit to participation, knowledge obtained from the survey has the potential to guide content development for an educational intervention targeting risk mitigation strategies for AP prescribing in the dental setting. This survey is intended to collect information regarding existing clinical practices pertinent to the specific patient populations and dental procedures for which AP is prescribed. This data will be collected to explore the necessity of further training, additional research and considerations during the next AHA guideline revisions.

3. OBJECTIVES

3.1. Study Objectives

3.1.1. Primary Objective

The primary objective of this study is to explore dentists' beliefs and behaviors related to AP guidelines and prescribing practices to prevent local or distant site infection after dental treatment.

3.1.2. Secondary Objectives

The secondary objectives of this study are to explore:

- Factors related to dentists' adherence to AP guidelines for the prevention of IE and PJI and their influence upon AP prescribing practices.
- Dentists' knowledge about risks for bacteremia and the utility of AP in preventing distant site infection.

3.2. Study Outcome Measures

3.2.1 Primary Outcomes

All data will be collected via an online survey management system. The primary outcome measures are dentists' a) beliefs, and b) behaviors related to AP guidelines and prescribing practices to prevent distant site infection.

Beliefs about AP guidelines will be ascertained with survey questions that address the clarity of AP guidelines: AP regimens, patient populations for whom AP is prescribed, dental procedures for which patients receive AP.

Dentists' prescribing practice behavior will be ascertained with questions that assess:

- The types of patient populations for whom AP is prescribed
- Dentists' adherence to guidelines when prescribing AP
- Whether the dentist consults with the patient's physician/surgeon and/or defers to the physician's/surgeon's decision regarding the need for AP; who provides the AP prescription

3.2.2 Secondary Outcomes

The following secondary outcome measures will be ascertained:

- Official resources, professional colleagues, personal preferences, and patient factors related to dentists' adherence to AP guidelines for the prevention of infective endocarditis (IE) and prosthetic joint infection (PJI)
- The influence of official resources, professional colleagues, personal preferences, and patient factors upon dentists' likelihood to change AP prescribing practices for the prevention of infective endocarditis (IE) and prosthetic joint infection (PJI)
- Dentists' knowledge about risks for bacteremia
- Dentists' knowledge about the utility of AP in preventing infection

The survey data will be merged with coded National Network enrollment data. Data will include basic practice information and practitioner demographics provided in the National Network Enrollment data.

4. STUDY DESIGN

This survey questionnaire is a cross-sectional study that is limited to National Dental PBRN dentists who are currently practicing. Approximately 4,000 dentists will be invited to participate (approximately 2,400 respondents expected for an anticipated 60% average response rate, or approximately 2,500 maximum should the response rate be higher). All Network members, at the limited or full participation level, who are general dentists or specialists (N~992) in Endodontics, Periodontics, Prosthodontics, Orthodontics, Pediatric Dentistry, Dental Public Health, Orthodontics, and Oral/Maxillofacial Surgery will be invited to participate. Oral Pathologists and Oral Radiologists will **not** be invited to participate, as they are rarely involved with issues regarding AP.

Based on previous survey research within the Network, we anticipate an approximately 60% completion rate on average. Westat Coordinating Center will be responsible for randomly selecting dentists from within each Network region. Network regional quotas will help to ensure that each region has adequate representation within the survey.

Participation involves the completion of the practitioner AP Prescribing Practices survey. Dentists will complete the survey online through the REDCap survey management system, or upon special request a paper version can be mailed by a study team member at the Coordinating Center to the individual through standard United States Postal Service (USPS), and returned to sender upon completion via a pre-stamped, "no postage necessary" envelope that will accompany the hard copy. The return envelopes will be pre-addressed to the attention of [name] (SPI), and data entry will be performed by one of the designated study team members at the Coordinating Center. The paper, or hard, copy of the survey will be identical to the web-based survey. Westat Coordinating Center will be responsible for providing the SPI with contact information (including active email addresses) for member dentists randomly selected for participation based on inclusion/exclusion criteria. Dentists will be invited via email. The AP Prescribing Practices survey data will be collected via an online survey instrument housed in the Carolinas Medical Center (CMC) REDCap survey management system (SMS).

Following the launch of the survey, approximately 50 of the initial survey responders will be randomly selected to complete the online survey again (approximately 2 weeks post initial completion) for test-retest reliability purposes.

Development and administration of the survey is detailed in Section 7.

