5.3. Strategies for Recruitment and Retention

Eligible dentists will be identified based on the criteria noted from their responses on the Enrollment Questionnaire. To reduce time burden on the Regional Coordinators (RCs), dentists will be recruited in 3 waves, detailed in *Section 6.1*. All eligible dentists will first receive a study invitation email from the SPI explaining the study and inviting them to participate. The invitation will include a unique link to the electronic version of the survey and will clearly state the recommended timeframe for survey completion. Non-responding dentists will be sent reminder emails at approximately 10-14-day intervals after receiving the survey invitation email. The CMC Coordinating Center will send these 2 reminder emails prior to initiation of reminder contact by the designated RCs. Invited participants who have not completed the survey within 7-10 days after the second reminder will receive their third reminder email from the RCs. Invited participants who still have not completed the survey after these 3rd reminder emails will receive reminder contacts (e.g., phone, fax, email, postal mailing, etc.) from their respective RCs to prompt

participation coupled with a reminder of their unique survey link. Invited dentists who have not responded within approximately 10 weeks (from the date the survey was sent to them) will be considered non-responders, and their survey links will be deactivated.

During recruitment, email invitations will be sent in 3 large sample size waves and adjusted by following the response rates live in REDCap. Representative sampling of generalists from the 6 National Dental PBRN regions will thereby be achieved to arrive at approximately 2,500 total surveys for analysis. The size and composition of the first large sample size wave of invitations will be determined based upon pilot data from approximately 40 respondents (preliminary ramp-up launch planned in Timeline). The adjustments will be made using a random generator tool to reduce bias.

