6. STUDY SCHEDULE

6.1. Stage 1 - Survey Component: Enrollment/Baseline

- Eligible dentists will be identified from responses to National Dental PBRN Enrollment Questionnaire by Westat and will be randomly selected for participation based on inclusion/exclusion criteria; Westat will deliver contact information and selected Enrollment Questionnaire data to the SPI.
- Dentists will be invited to complete an online survey in 3 waves of increasing size to adjust for a balanced regional representation.
- Completion of the survey will indicate that practitioners have read informed consent information and will imply consent. A waiver of signed consent will be sought from the IRB.

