11.2. Sample Size Considerations

All objectives of the current study are either descriptive or exploratory - rather than hypothesis testing - in nature. Therefore, standard sample size calculations based on anticipated effect sizes do not apply. However, based on a survey quideline report by Brinkman W-P et al.*, our proposed sample size will allow us to perform statistical analyses for observed small to medium effect sizes (comparing general dentists to specialists, all categories included) and for medium to large effect sizes (specialist subcategories). Our sample size was selected based on the total number of dentists available as of January 7th 2017 (N=4002 including 3002 general dentists (GDs) and 992 specialists, excluding the category "other", see Table 1 below). Our 3-pronged recruitment approach will ensure comparable representation of both general and specialist dentists from all National Dental PBRN regions and minimize the margin of error to compare generalists with specialists overall or to compare some of the specialist subcategories (e.g. pediatric dentists vs. non-pediatric specialists). Table 1 below presents National Dental PBRN enrollment data for each region from Jan 7, 2017. Table 2 presents the number of invited participants and anticipated number of completing participants, per each dentist or region category with respective survey margins of error (MOE) at 95% confidence level. Proposed sample size allows for a margin of error of 3.15% (+/- 0.34 (SD)) on average per region (generalists and specialists combined),

0.05% for general dentists and 2.55% for specialists (all regions combined), at 95% confidence level. The online tool (https://www.qualityoutcomes.com/samplesize.aspx) was used to determine whether samples size per region or per specialty were appropriate to allow for minimal MOE possible.

* Preliminary version of: Brinkman, W-P (2009). Design of a Questionnaire Instrument, Handbook of Mobile Technology Research Methods, ISBN 978-1-60692-767-0, pp. 31-57, Nova Publisher.

Table 1. National PBRN Enrollment as of Jan 7th 2017

					Specialists subcategories							
Region	Dentists	Total Dentists	GDs	SPs	Total SPs	Endo-	Pediatric	Perio-	Prostho-	Oral/Maxillo-	Ortho-	
	all PBRN	w/o "Other"			w/o Other	dontist	Dentist	dontist	dontist	facial Surgeon	dontist	
1. Western	599	583	415	184	168	22	21	11	6	7	101	
2. Midwest	494	481	350	144	131	19	23	17	12	8	52	
Southwest	797	783	594	203	189	27	36	43	11	19	53	

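### The protocol invites every eligible member but also prescribes regional quotas, waves adjusted to response and a maximum near 2,500; if these limits are applied, invitation chances become unequal and the stated weighting does not account for it

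*Protocol*

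**What the plan says.** Two descriptions of who is invited stand side by side in the Protocol.

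**Everyone.** Section 4 opens the invitation to "All Network members, at the limited or full participation level, who are general dentists or specialists (N~992" in the listed specialties, and gives the number: "Approximately 4,000 dentists will be invited to participate". Section 5.3 agrees: "All eligible dentists will first receive a study invitation email from the SPI explaining the study and inviting them to participate". Section 11.2 bases the sample size on the whole membership available on 7 January 2017, "N=4002 including 3002 general dentists (GDs) and 992 specialists". (Table 1 has 3,010 general dentists, which with 992 specialists does add to 4,002.)

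**A selected subset.** Section 4 also states "Westat Coordinating Center will be responsible for randomly selecting dentists from within each Network region" and refers to regional quotas without giving their size. Section 6.1 repeats the random selection and describes "3 waves of increasing size to adjust for a balanced regional representation". Section 5.3 says that "email invitations will be sent in 3 large sample size waves and adjusted by following the response rates live in REDCap", using a random generator. Section 4 expects about 2,400 respondents, "or approximately 2,500 maximum should the response rate be higher".

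**Analysis.** The Final Analysis Plan defines total non-response among dentists who were sent a survey link. It compares respondents and non-respondents on demographic and practice characteristics, including specialty and practice location. Weights are applied if significant demographic differences appear, and main outcomes are then analysed both weighted and unweighted.

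**The concern.** If about 4,000 of 4,002 dentists are invited, nobody is left to select, to fill a quota with or to rebalance from. If the quotas, the response-driven waves or the maximum do operate, some eligible members are never invited, and which ones depends on region and on how earlier waves responded.

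The study's product is a set of descriptive estimates for network dentists. Whether the completers are a census with non-response or a sample with unequal selection decides three things: the denominator of the response rate, whether the stated margins of error describe what was done, and which weights are needed. Invitation probabilities are hard to reconstruct after ad hoc adjustment, so the choice has to be made before launch.

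**Working it through.** **1. Do the protocol's own figures assume that everyone is invited?** Inputs are the Table 1 totals without the category Other, the 60% response rate, and Table 2.

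Expected completers are n = 0.60 × N. The margin of error with finite population correction is 1.96 × √(0.25/n) × √((N − n)/(N − 1)).

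| Region | N | 0.60 × N | Table 2 n | MOE computed, % | MOE stated, % |
|---|---|---|---|---|---|
| Western | 583 | 349.8 | 350 | 3.31 | 3.33 |
| Midwest | 481 | 288.6 | 289 | 3.65 | 3.65 |
| Southwest | 783 | 469.8 | 469 | 2.87 | 2.87 |
| South Central | 744 | 446.4 | 446 | 2.94 | 2.94 |
| South Atlantic | 577 | 346.2 | 346 | 3.34 | 3.34 |
| North East | 834 | 500.4 | 500 | 2.78 | 2.78 |
| All | 4,002 | 2,401.2 | 2,400 | 1.27 | 1.27 |

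For the total: 1.96 × √(0.25/2,400) = 2.00%, and 2.00% × √(1,602/4,001) = 1.27%. Without the correction the overall figure would be 2.00%. So Table 2 takes the full membership as its population and needs about 2,400/0.60 = 4,000 invitations out of 4,002. (The 0.05% stated for general dentists does not reproduce; the same formula gives 1.46%. That is a separate matter.)

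**2. When does the maximum bind?** 2,500/4,002 = 62.5% response. At the planned 60% it does not. At an assumed 70%:

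- inviting everyone gives 0.70 × 4,002 = 2,801 completers, about 301 beyond the maximum; or
- stopping at 2,500 needs 2,500/0.70 = 3,571 invitations, which leaves 4,002 − 3,571 = 431 members uninvited.

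The text does not say which would happen. At assumed responses of 65% and 80%, the uninvited would number 156 and 877.

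**3. How unequal could inclusion become?** This depends on quotas that the protocol does not give.

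- Quotas proportional to Table 2: completion is about 60% in every region, so regions are nearly equal.
- Equal quotas of 400 per region (assumption): completion fraction is 400/481 = 0.83 in the Midwest and 400/834 = 0.48 in the North East, a ratio of 834/481 = 1.73. The Kish design effect is 6 × ΣN²/(ΣN)² = 6 × 2,766,360/4,002² = 1.036. The Midwest could not reach 400 at 60% response, so this marks an outer case.
- A ceiling of 2,500/6 = 417 per region (assumption): at 60% response, the fraction invited runs from 1.00 in the three smallest regions to 417/(0.60 × 834) = 0.83 in the North East. Completion fractions then range 1.20-fold, with a design effect of about 1.005. At 70% the lowest fraction invited is 0.71, the range 1.40-fold and the design effect about 1.02.

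**4. Would the stated weighting correct this?** A member who was never sent a link is neither a respondent nor a non-respondent under the Final Analysis Plan, so falls outside the comparison. The trigger for weights is a demographic difference. Specialty and location are compared, but a difference in them alone is not the stated trigger. Invitation probability is not used.

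**The case against.** The strongest reply is that the texts can largely be reconciled. Section 5.3 gives Regional Coordinator workload as the reason for the waves and says that adjustments use a random generator. Read that way, everyone is invited and randomness only sets the order. This stands for random ordering. It does not extend to quotas, to composition driven by response or to a binding maximum, because each of these matters only if someone is left out.

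Other parts of the defence also stand and limit the point:

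- A reader might infer that late completers are turned away at 2,500. No section says so. The figure sits in a parenthesis on expected yield, the Protocol Summary words it without calling it a maximum, and the only closing rule is about 10 weeks from each dentist's own invitation.
- A reader might take balanced regional representation to mean equal numbers, in conflict with the proportional Table 2. The protocol also speaks of adequate and representative coverage, which fits proportional allocation.
- A reader might combine the 4 months of enrolment with the 10-week window and infer a launch deadline for the last wave. The 4 months is an estimate, the implementation phase is 9 months, and live monitoring does not need a completed first wave.
- A reader might infer that about 40 pilot respondents are too few to set the first wave by region. Any figure for this needs an assumed pilot response and regional split, and the size of the first wave does not affect inclusion if all are eventually invited.
- The frame is not exactly settled: the Protocol Summary gives 4,084 and Table 1 gives 4,082 with Other. With 4,084 the maximum binds at 61.2%, so the argument is unchanged.

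Finally, weight construction may be left to a statistical analysis plan. Whom to invite may not: it is carried out before any analysis, and the weighting rule that the protocol does state leaves selection out.

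**Conclusion.** The contradiction is real and should be fixed, but it does not show that any estimate will be wrong. The sample sizes and margins of error rest on inviting all of about 4,002 members. The quotas, response-driven composition and maximum describe something else, and the stated weighting would not correct for it.

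The effect is conditional. At 60% response with proportional quotas it is close to nil. Under equal quotas, an assumption, completion fractions range up to 1.73-fold, but the design effect of about 1.04 shows that precision is hardly touched. What is at risk is bias if regions differ in prescribing beliefs or behaviour, together with an unclear denominator. The maximum matters only above 62.5% response.

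**What to change.** In Sections 4, 5.3 and 6.1, state that all eligible members are invited. Randomise them to the three waves within strata of region by general dentist/specialist, and use the waves only to spread Regional Coordinator workload. Remove the regional quotas, the response-driven adjustment of wave composition and the 2,500 maximum. Low response in a region can still be met with the reminder contacts already planned.

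If selection or a maximum is kept, define it as a random stratified hold-back, record each member's invitation probability, and apply inverse-probability base weights in addition to the non-response weights.

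The cost is protocol wording, plus the $50 payment in Section 5.3 for each completer above 2,500. At an assumed 70% response that is 301 × $50, about $15,000; at the planned 60% it is nothing.

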5. STUDY ENROLLMENT AND WITHDRAWAL

5.1. Inclusion Criteria

A participant must meet following criteria:

- Is enrolled in the National Dental PBRN as a limited or full network member;
- Is a dentist licensed in the U.S. and is actively engaged in practice.

5.2. Exclusion Criteria

A dentist practitioner meeting the following criteria will be excluded from the study:

• Endorses specialty practice ONLY in Oral Radiology or Oral Pathology.

5.3. Strategies for Recruitment and Retention

Eligible dentists will be identified based on the criteria noted from their responses on the Enrollment Questionnaire. To reduce time burden on the Regional Coordinators (RCs), dentists will be recruited in 3 waves, detailed in *Section 6.1*. All eligible dentists will first receive a study invitation email from the SPI explaining the study and inviting them to participate. The invitation will include a unique link to the electronic version of the survey and will clearly state the recommended timeframe for survey completion. Non-responding dentists will be sent reminder emails at approximately 10-14-day intervals after receiving the survey invitation email. The CMC Coordinating Center will send these 2 reminder emails prior to initiation of reminder contact by the designated RCs. Invited participants who have not completed the survey within 7-10 days after the second reminder will receive their third reminder email from the RCs. Invited participants who still have not completed the survey after these 3rd reminder emails will receive reminder contacts (e.g., phone, fax, email, postal mailing, etc.) from their respective RCs to prompt

participation coupled with a reminder of their unique survey link. Invited dentists who have not responded within approximately 10 weeks (from the date the survey was sent to them) will be considered non-responders, and their survey links will be deactivated.

During recruitment, email invitations will be sent in 3 large sample size waves and adjusted by following the response rates live in REDCap. Representative sampling of generalists from the 6 National Dental PBRN regions will thereby be achieved to arrive at approximately 2,500 total surveys for analysis. The size and composition of the first large sample size wave of invitations will be determined based upon pilot data from approximately 40 respondents (preliminary ramp-up launch planned in Timeline). The adjustments will be made using a random generator tool to reduce bias.

To minimize access to survey response data, the SPI will communicate with RCs regarding nonresponders through the use of password protected excel spreadsheets that do not contain survey response data. The SPI will deliver updated completion reports to RCs on a regular basis to minimize unnecessary contact with invited participants who have already completed the survey. In addition, the SPI will hold regular Study Team calls to troubleshoot any issues that may arise with study recruitment efforts.

Dentists completing the survey will be remunerated with \$50 delivered via email to their active email addresses or other means (e.g., postal mail) if required. This is a cross-sectional survey study; retention strategies are not applicable. However, approximately 50 participating dentists will complete the online survey a second time to establish test-retest reliability. Dentists completing the test/retest will be compensated an additional \$50 for their participation.

